Vaccine coverage (number vaccinated divided by the number eligible for vaccine) will be measured using pharmacy database analysis, public health vaccine reports by physicians, vaccine doses delivered (in all four regions), and by public survey within the study communities (part of the KABB survey). Statistics Canada census data from 2015 will be used to determine the denominator for those eligible for the vaccine by 5-year age groups.

3. Adverse Events Following Immunization Reporting (AEFI)

Using the Canadian National Vaccine Safety Network (CANVAS)'s surveillance system for adverse events following seasonal influenza vaccination, we will compare the proportions of eligible individuals who register for CANVAS and complete the online AEFI survey among pharmacies using active recruitment strategies (e.g., handing out information sheets and registration forms) and those using passive recruitment strategies (e.g., displaying posters and information sheets).

Sample Size
 There are four communities involved in the study, Saint John and Moncton, New Brunswick and New Glasgow/Pictou/Antigonish and Kentville/Wolfville/New Minas, Nova Scotia. All participating pharmacies in each community will be allocated either to the bundled pharmacist-delivery intervention or to standard care (control arm). Residents in each community will receive a KABB survey, regardless of whether or not they were vaccinated as part of this study. Information and registration forms

ROMEO File #: 1021559

for CANVAS surveillance will be actively distributed to those who received influenza vaccines in the intervention communities and information on CANVAS will be displayed at pharmacies in control communities. A sample size of 400 for the KABB survey will provide a margin of error of less than 5% for estimated proportions. For vaccine coverage, a separate sample size of 596 per group will provide power of at least 80% to detect superiority.

Endpoints Outcomes/analysis plan/sample size/statistics Outcomes

- 1. Population-specific vaccine coverage before and after programimplementation interventions.
- 2. Proportion of population in intervention districts whose supplementary health benefit plans cover studied vaccines.
- 3. Public KABB about vaccine-preventable diseases and related vaccines before and after program-implementation interventions.
- 4. Public willingness to pay and co-pay for studied vaccines.
- 5. Healthcare providers KABB regarding pharmacist- delivered vaccine programs.

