1.5 Pharmacists as Immunizers

Patients are typically educated about preventative health care during face-to-face visits with physicians in office settings, or in the case of vaccines, by nurses at vaccination appointments. The ability to educate and deliver preventative health care is limited by the available provider time during client visits. Providers note that the time to provide vaccine education is considerable, and clients' acute needs and current disease management generally take priority. New delivery models and a means of extending preventative health care delivery outside of traditional face-to-face office visits are needed (Yarnall, 2003).

Pharmacists are in a unique position of being among the most accessible of health professionals (Canadian Pharmacists Association, 2012). In a study of the attitudes and beliefs of the Canadian public on routine immunization by pharmacists, pharmacists were identified as a trustworthy source of health information, similar to public health officials and exceeded only by family doctors and nurses (MacDougall et al., 2016). Given their extended operating hours, accessibility, and established trust with patients, pharmacists are well-positioned to improve vaccination rates and health system efficacy through injection administration (Houle, 2013) Moreover, people regularly visit community pharmacies for their health care needs, particularly in rural settings, due to extended hours and convenient locations (Kau, 2011). In addition, through their interaction to fill prescriptions and education patients about their use, pharmacists have regular contact with high-risk individuals and are able to proactively and systematically review patients' medical histories and medications, and remind them about the benefits of vaccination. Such interventions have been shown to have a significant impact on a person's decision to be immunized, similar to the impact of a recommendation from a physician or nurse (Grabenstein, 1992).

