Pharmacy databases will be used to determine the number of doses administered to individuals relative to the total number of clients in the pharmacy database in the eligible age range. The total number of doses administered by pharmacists (from their database) plus the number administered by family physicians, through study-specific reciprocal notification forms, will also be calculated and compared to

ROMEO File #: 1021559

the Statistics Canada population age-specific census data for the community will also be calculated. The study-specific system of reciprocal notification forms for family physicians will be implemented so that it is similar to that used for publicly funded routine pediatric vaccines. Another estimate of vaccine coverage will be vaccine doses distributed to pharmacies in the participating communities (obtained from the manufacturer and Public Health) relative to the eligible population based on Statistics Canada census data from 2016. Specific questions about receipt of target vaccines will be added to the KABB survey that will be administered pre- and post-intervention. These questions will be modeled on a 2014 study performed by the Vaccine Evaluation Center (Schneeberg, 2014). The KABB survey will also include specific questions about willingness to pay to inform decisions about co-payment funding models for recommended adult vaccines.

Outcomes

As a result of this study:

- 1. Population specific vaccine coverage will be documented before and after program implementation interventions.
- 2. The proportion of the population in intervention districts whose supplementary health benefit plans cover studied vaccines will be identified.
- 3. The public willingness to pay and co-pay for studied vaccines will be better known and understood.

For specific outcomes related to each targeted vaccine, see appendices.

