3.2 Knowledge, attitudes, beliefs and behaviours

This study will use one survey to assess the KABB of community-dwelling adult members of the public regardless of whether or not they were vaccinated as part of this study and a second survey for physicians, pharmacists, and vaccine providing nurses (e.g. family practice nurses, public health nurses, and nurse practitioners). Surveys will be distributed before and after the intervention regarding knowledge, attitudes, beliefs, and behaviours of targeted study vaccines and their delivery by pharmacists.

Questions included on surveys to assess the KABB of the public will focus on awareness of vaccines availability, attitudes toward vaccines, perceived social pressures to vaccinate, ability to access vaccination, intention to vaccinate, the use of pharmacists as immunizers and willingness to pay for vaccines. Questions included on surveys to assess the KABB of health practitioners will focus on logistics of vaccine delivery and record keeping, attitudes toward vaccines, beliefs about pharmacists as immunizers, support of the current age restriction for pharmacist delivery (children 5 years of age and older in Nova Scotia and New Brunswick) and current immunization practices.

It is hypothesized that knowledge about the vaccines being studied is lower among the general public and higher among practitioners. This study also hypothesizes that there is a high level of support among both the public and health care providers for pharmacists as immunizers. Knowledge and support amongst both providers and the public is expected to increase after the implementation of the

ROMEO File #: 1021559

intervention study.

KABB Questionnaire Theoretical Model

Participation in health protective behaviours, such as vaccination, is influenced by psychological factors, many of which are part of greater behavioural change theories (Gerend, 2012). The theory of planned behaviour (TPB) is a theoretical framework that explains the causal chain linking behavioural beliefs, normative beliefs and control beliefs to the formation of intention, presumed to be the immediate antecedent of behaviour (Glanz, 2015; Ajzen, 1986). Intended to explain deliberative actions based on these constructs, the TPB is well positioned to predict immunization, however lacks specificity in healthcare decision making (Corace, 2016).

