determined by physician billing data and public health provision of vaccine to physicians relative to the Statistics Canada population age specific census data for that community. A study-specific system of reciprocal notification forms for family doctors will be implemented that is similar to that used for publicly funded routine vaccines. A third estimate of vaccine coverage will be vaccine doses distributed in the participating communities (obtained from the manufacturer) relative to the eligible population based on Statistics Canada census data (2011 and 2016 when available). The fourth estimate of vaccine coverage will be derived from the pre- and postprogram public survey. Binomial point estimates and confidence intervals will be made for vaccine coverage rate within site, and coverage will be compared between and among sites using confidence intervals for the difference of binomial proportions, Fisher's exact tests, and logistic regression. Using a margin of superiority of 10%, when comparing two coverage proportions within site or between sites, a sample size of 298 per group gives 80% power to conclude in favor of superiority when the true difference in proportions is at least 20%, and a sample size of 1209 per group provides 80% power when the true difference in proportions is at least 15%, assuming independent responses. However, it is anticipated that there will be dependence within the family unit regarding the decision to be vaccinated, in which case the precision on the binomial point estimate, and thereby, the required sample size, depends on the size of the family unit and the intraclass correlation. Assuming the family unit to consist of two adults, and under the worst-case scenario in which the decision on vaccination is fully concordant for the two family members, the required sample size per group to detect a specified difference is doubled, to 596 (2418) when the true difference is at least 20% (15%). Estimates of the intraclass correlation will be calculated using data from pharmacy databases and from the public survey portion of the study, and these will be used to adjust confidence intervals and test statistics to accommodate within family dependence (Donner, Brikett, & Buck, 1981).

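### One census-based coverage estimate counts only pharmacist and family-physician doses, so a switch from a nurse or public health clinic to a pharmacist would register as new coverage

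*Combined protocol and SAP*

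**What the plan says.** The Synopsis, under outcome measure 2, defines the quantity of interest: "Vaccine coverage (number vaccinated divided by the number eligible for vaccine". Section 3.1 then describes several ways to estimate it. One is a combined count: "The total number of doses administered by pharmacists (from their database) plus the number administered by family physicians", set against "the Statistics Canada population age-specific census data for the community". The family-physician part comes from a purpose-built form: "The study-specific system of reciprocal notification forms for family physicians will be implemented". The public health reports listed as a source, in both the Synopsis and section 3.1, are likewise reports made by physicians.

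In section 6.2, the second estimate is "determined by physician billing data and public health provision of vaccine to physicians", again over the census population.

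Elsewhere the protocol recognises further vaccinators. Section 3.2 surveys "vaccine providing nurses (e.g. family practice nurses, public health nurses, and nurse practitioners", and section 1.5 says that patients are educated, "in the case of vaccines, by nurses at vaccination appointments". Neither 3.1 nor 6.2 names a form, register or data request for doses given by nurses or public health clinics.

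**The concern.** The numerator of the combined count covers two provider types, while its denominator is the whole age-eligible population. Anyone vaccinated elsewhere is in the denominator and is treated as unvaccinated. This has two consequences.

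- **Level.** The figure is lower than coverage as the Synopsis defines it.
- **Change.** A resident who would have gone to a public health nurse, but goes to a pharmacist instead, adds one to the numerator although the community's coverage has not moved.

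A constant undercount would be largely shared by both periods and all four communities. Switching would not. Free Tdap, the co-pay arrangement and pharmacy mail-outs or calls operate through pharmacies in the intervention communities only, so the control communities cannot be relied on to cancel it. The question for funders is whether pharmacist delivery adds vaccinations or only relocates them, and on this point the combined count cannot tell the two apart.

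**Working it through.** **1. The estimates side by side**

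| Estimate | Numerator as worded | Does a nurse-to-pharmacist switch raise it? |
|---|---|---|
| Pharmacy database (3.1, 6.2) | Pharmacy doses, over pharmacy clients | Yes, but it is openly a pharmacy measure |
| Combined count (3.1) | Pharmacist plus family-physician doses, over census | Yes |
| Second estimate (6.2) | Physician billing and supply to physicians, over census | Not as worded; it does not supply the missing doses either |
| Distributed doses (3.1) | Doses supplied to pharmacies, over census | Yes |
| Distributed doses (6.2) | Doses supplied to the communities, no provider limit | No |
| Public survey (3.1, 6.2) | Self-reported receipt, any provider | No |

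**2. One resident followed through the combined count**

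Vaccinated by a public health nurse: true status 1, counted 0. Vaccinated instead by a pharmacist: true status 1, counted 1. True change 0, counted change +1.

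**3. The plan's own figures**

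The plan gives no figure for the share of doses by provider. Its sample sizes show how the 10% is meant. The formula is n = [p1(1−p1) + p2(1−p2)] × (z_α + z_β)² / (difference − 0.10)². I used one-sided alpha 0.05, 80% power and proportions centred on 0.5, all inferred except the power. Then (z_α + z_β)² = 6.1826.

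- True difference 20% (0.40 vs 0.60): 0.48 × 6.1826 / 0.10² = 296.8, so 297 against the stated 298.
- True difference 15% (0.425 vs 0.575): 0.48875 × 6.1826 / 0.05² = 1208.7, so 1209, as stated.

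The margin is therefore in absolute percentage points, and I read the 10% criterion the same way. These sample sizes do not depend on which providers are counted.

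**4. Size of the error**

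Inputs, all assumed:
- c0, baseline coverage: 8%. Section 1.2 says only that adult Tdap coverage is thought to be well below 10%.
- s, share of doses from uncounted providers: 10% to 40%.
- m, fraction of those recipients who switch to a pharmacist: half or all.

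Level shown = c0 × (1 − s). Spurious rise = c0 × s × m, with zero true change.

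| s | Level shown | Rise, m = 0.5 | Rise, m = 1 |
|---|---|---|---|
| 10% | 7.2% | 0.4 points | 0.8 points |
| 20% | 6.4% | 0.8 points | 1.6 points |
| 40% | 4.8% | 1.6 points | 3.2 points |

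At an assumed 20% baseline with half switching, the rises are 1.0, 2.0 and 4.0 points. If every provider is counted, the rise is 0 in each case.

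**5. What it would take to reach 10 points**

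Switching alone needs c0 × s × m of at least 10%. That would be 20% of the eligible population vaccinated by uncounted providers with half switching, or 10% with all switching. At an 8% baseline it cannot happen: the ceiling is 8% × 1 × 1 = 8 points.

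**The case against.** The strongest reply is that this is one of several parallel estimates and that others escape the error. That stands. A reader might infer that every source in section 6.2 is limited to physicians. The same paragraph, however, also has doses distributed in the communities without a provider limit, and the public survey. A reader might also take the combined count for the plan's all-provider or principal measure, but the documents give it neither status and name no estimate as primary. The alternatives have limits of their own: the survey is self-reported and recruited by open advertisement, and section 3.1 words distributed doses as pharmacy supply only.

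It is also too strong to say that no nurse's dose is counted. A family practice nurse's doses may be reported on the practice's physician form; the text does not say. The gap is firmer for public health nurses, nurse practitioners and public health clinics.

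The evidence on volume is thin. The section 1.5 sentence is about educating patients, section 3.2 defines who is surveyed, and most of the study vaccines are described as unfunded or privately bought. That stands, and it is why the size is left open.

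The direction is not wholly one-way. Outreach could also prompt vaccination by a nurse, and missing those doses would work against the intervention. That stands as a possibility, although the price terms apply at pharmacies.

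Finally, section 3.1 refers to appendices for vaccine-specific outcomes, and Appendices A to E are not available. A vaccine-specific source for nurse or clinic doses cannot be ruled out.

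**Conclusion.** The point holds for the combined census-based count. Followed as written, it understates coverage as the Synopsis defines it and turns a switch from an uncounted provider to a pharmacist into apparent new coverage, mainly in the intervention communities. The second estimate in 6.2 does not close the gap.

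The size is unknown and rests wholly on assumed values for baseline, omitted share and switching. A reader might infer that switching could by itself deliver the hypothesised increase. The documents do not support that: they give no nurse or clinic volumes, and on the range worked here the error stays well under 10 points. It matters because a shift of a point or more can tip a result near the criterion, and because no rule says which estimate decides the matter or how the estimates are reconciled. The change is worth making, but the point does not undermine the coverage objective as a whole.

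**What to change.** - In sections 3.1 and 6.2, define the numerator of the census-based estimates as doses from all vaccinating providers.
- Extend the planned notification form and the public health data request to vaccine-providing nurses and public health clinics, in all four communities and for the same periods. State whether family practice nurses' doses belong on the physician's form.
- Where those counts cannot be had, label the figure as pharmacist plus family-physician doses per population and do not use it to judge the 10% increase. Read it beside the survey and the community-wide distributed-dose estimate, after reconciling the 3.1 and 6.2 wording of the latter.
- The draft questionnaire is not visible. If the survey does not already ask who gave each vaccine, add that item and use the provider mix as a sensitivity check.

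The cost is small: protocol wording, a wider mailing of a form already planned, a wider data request and perhaps one survey item. The downside is some added reporting by nurses and clinics.

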3.2 Knowledge, attitudes, beliefs and behaviours

This study will use one survey to assess the KABB of community-dwelling adult members of the public regardless of whether or not they were vaccinated as part of this study and a second survey for physicians, pharmacists, and vaccine providing nurses (e.g. family practice nurses, public health nurses, and nurse practitioners). Surveys will be distributed before and after the intervention regarding knowledge, attitudes, beliefs, and behaviours of targeted study vaccines and their delivery by pharmacists.

Questions included on surveys to assess the KABB of the public will focus on awareness of vaccines availability, attitudes toward vaccines, perceived social pressures to vaccinate, ability to access vaccination, intention to vaccinate, the use of pharmacists as immunizers and willingness to pay for vaccines. Questions included on surveys to assess the KABB of health practitioners will focus on logistics of vaccine delivery and record keeping, attitudes toward vaccines, beliefs about pharmacists as immunizers, support of the current age restriction for pharmacist delivery (children 5 years of age and older in Nova Scotia and New Brunswick) and current immunization practices.

It is hypothesized that knowledge about the vaccines being studied is lower among the general public and higher among practitioners. This study also hypothesizes that there is a high level of support among both the public and health care providers for pharmacists as immunizers. Knowledge and support amongst both providers and the public is expected to increase after the implementation of the

ROMEO File #: 1021559

intervention study.

KABB Questionnaire Theoretical Model

Participation in health protective behaviours, such as vaccination, is influenced by psychological factors, many of which are part of greater behavioural change theories (Gerend, 2012). The theory of planned behaviour (TPB) is a theoretical framework that explains the causal chain linking behavioural beliefs, normative beliefs and control beliefs to the formation of intention, presumed to be the immediate antecedent of behaviour (Glanz, 2015; Ajzen, 1986). Intended to explain deliberative actions based on these constructs, the TPB is well positioned to predict immunization, however lacks specificity in healthcare decision making (Corace, 2016).

The health belief model (HBM) was developed in the 1950s by social psychologists in the U.S. Public Health Service in an attempt to understand the common failure of people to accept disease preventives or screening for the early detection of disease (Edberg, 2010). According to the model, engagement in health action rests on the belief that such action can reduce a threat that is both likely and would have severe consequences (Glanz, 2015). The constructs that predict whether and why an individual will take action to prevent, detect or control illness conditions according to the HBM, include perceived susceptibility, severity, benefits and barriers to engaging in health actions, cues to action, and self-efficacy (Glanz, 2015).

There is considerable correlation between the HBM and the theory of planned behaviour (TPB) proposed by Ajzen and Timko (1986). Both theories are based on the same framework, make similar assumptions, have overlapping constructs and adopt an individual level approach to predicting health behaviour. The primary difference between them is that the TPB contains a proximate predictor of behaviour or an intention to act, where the HBM does not (Gerend, 2012). The combination of both of these theories is beneficial to this study because it will allow a broad understanding of the intent to vaccinate in addition to vaccine-specific perceptions of barriers and facilitators that will help focus future intervention. A blended TPB and HBM survey design from a 2014 study led by the Vaccine Evaluation Center along with members at the Canadian Center for Vaccinology (Schneeberg, 2014), will inform the selection of questions for the proposed survey in addition to relevant literature.

Survey Design and Study Population

This study will use repeated cross-sectional online surveys to assess the KABB of community-dwelling adult members of the public regardless of whether or not they were vaccinated as part of this study and a second survey for physicians, pharmacists, and vaccine providing nurses. Surveys will be distributed before and after the intervention regarding knowledge, attitudes, beliefs, and behaviours of targeted vaccines and their delivery by pharmacists.

For the community public surveys, all individuals >18 years of age in the intervention and control communities in Nova Scotia and New Brunswick will be eligible regardless of whether or not they were vaccinated as part of this study. Adult residents in all four participating communities will be informed about the survey and invited to participate by means of local advertisements in community print and online publications, posters, via social media, and through information distributed in the community pharmacies. These advertisements will contain the web address where the online KABB survey can be found.

ROMEO File #: 1021559

For the healthcare provider survey, all family physicians, pharmacists and vaccine providing nurses in Nova Scotia and New Brunswick will be eligible. In order to increase national generalizability, we will examine the logistics of partnering with investigators in other provinces to administer the surveys in their jurisdictions. Pharmacists and vaccine providing nurses in all four participating communities will be informed about the survey and invited to participate by means of local advertisements in print and online publications distributed by professional associations (such the Neighborhood Pharmacy Association) via available social media (e.g. Facebook groups and Twitter accounts with permission), posters on internal bulletin boards in local hospitals, and other publicly available means such as targeted outreach via email (e.g., publicly posted email addresses for clinics, pharmacies, etc.). Locally, physicians will be recruited for the KABB survey through the regional hospital medical staff offices. Provincially, physicians will be recruited through Doctors Nova Scotia. These advertisements will contain the web address where the online KABB survey can be found.

Questions to assess the KABB of the public will focus on awareness of vaccines available, attitudes toward vaccines, perceived social pressures to vaccinate, ability to access vaccination, intention to vaccinate, the use of pharmacists as immunizers, willingness to pay for vaccines, and current vaccination status for study vaccines. The health care provider survey will collect information on physicians', nurses' and pharmacists' KABB regarding logistics of vaccine delivery and record keeping, current immunization practices, attitudes toward vaccines, burden of illness associated with vaccine-preventable diseases, pharmacists as immunizers, and the current age restriction (children 5 years of age and older). Educational needs of healthcare providers on the conditions linked to the vaccinations and their prevention will be collected as well.

The public and provider surveys will be distributed accordingly during the 6-month period prior to implementation of the community-wide pharmacy intervention and immediately following the two-year intervention. KABB survey data will be available and collected prior to flu season.

Survey Instruments Development

Validated survey instruments (questionnaires) will be developed using a formative process informed by Ajzen and Timko in the TPB with target constructs from the HBM. Survey instruments will include two different questionnaires and will be distributed twice according to the above timeline:

- 1. The questionnaire for the public contains approximately 50-60 yes or no, or strength of agreement questions using a Likert scale measuring attitudes toward vaccines, perceived social pressures to vaccinate and perceived/actual behavioural controls. More specifically, data collection will include demographic information, perceived susceptibility and severity of illnesses, perceived benefits and barriers to vaccination, intention to vaccinate, educational needs on prevention and protection, use of pharmacists as immunizers and willingness to pay for vaccines. A draft list of questions has been attached; these questions will be modified, reduced in number, and appropriately ordered prior to finalization. The final survey instrument will be resubmitted to the REB for approval.
- 2. The questionnaire for health care providers will contain approximately 30-40 yes or no, or strength of agreement questions using a Likert scale measuring knowledge, attitudes and beliefs about the logistics of vaccine delivery and record-keeping, current immunization practices, attitudes toward vaccines, burden of illness associated with vaccine-preventable

ROMEO File #: 1021559

diseases, pharmacists as immunizers, and the current age restriction (children 5 years of age and older). A draft list of questions has been attached; these questions will be modified, reduced in number, and appropriately ordered prior to finalization. The final survey instrument will be resubmitted to the REB for approval.

The survey instruments will be constructed following the principles of survey design of Dillman, Smyth, and Christian (2014). Previously validated questions will be employed whenever possible. Statistical analysis will be done with SAS version 9.4 by the Data Management Group at the Canadian Center for Vaccinology (CCfV). Prior to distributing the survey, the content validity of individual questions, as well as the content validity of the entire questionnaire, will be evaluated by a panel of experts comprised of nurses, pharmacists, and infectious diseases physicians and vaccinologists at CCfV. The panel will determine the content relevance of the questions and the questionnaires as a whole using a rating worksheet. Each item will be rated using a standard content validity index with a 4-point ordinal rating scale, where 1 indicated irrelevance and 4 highly relevant. Items that receive a score of 3 or 4 will be judged to have content validity. The content validity index for the entire instrument will be the proportion of items judged to have content validity. Items that do not achieve the required minimum agreement of experts will be eliminated or revised. Test-retest reliability will be assessed by having up to five health care providers and 5 members of the public complete the questionnaires at two different points in time (approximately 14 days apart). A correlation co-efficient will be calculated to compare the two sets of responses; questionnaire responses with a coefficient > 0.70 will be interpreted as consistent.

Remark[®] software will be used. The database will be accessible through a secure web application with personal passwords for research staff. All participant information will be stored in Remark[®] and contact information will only be available to authorized staff (e.g., study nurse).

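### A retest in at most five people per questionnaire, read against a 0.70 correlation cut-off, cannot support calling the KABB responses consistent

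*Combined protocol and SAP*

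**What the plan says.** Section 3.2 of the combined protocol and SAP, under Survey Instruments Development, describes two questionnaires. The public one has "approximately 50-60 yes or no, or strength of agreement questions using a Likert scale"; the provider one has "approximately 30-40 yes or no, or strength of agreement questions using a Likert scale". The section introduces them with the words "Validated survey instruments (questionnaires) will be developed using a formative process".

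The check of repeatability reads: "Test-retest reliability will be assessed by having up to five health care providers and 5 members of the public complete the questionnaires" on two occasions, "approximately 14 days apart". The analysis is one sentence: "A correlation co-efficient will be calculated to compare the two sets of responses", and "questionnaire responses with a coefficient > 0.70 will be interpreted as consistent".

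The plan does not name the coefficient. It does not say whether it is computed per item, per respondent or over the whole questionnaire. It asks for no interval and no measure of agreement, and it gives no consequence for a value of 0.70 or below. The other development steps are an expert panel that rates content relevance and the reuse of previously validated questions where possible.

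**The concern.** Change in KABB is the second primary objective (Section 2.1). The surveys are repeated cross-sections (Section 3.2) and anonymous (Section 5.1), so the main data cannot later show whether a person answers the same way twice. The five-person retest is the only planned check of repeatability.

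Three features make its verdict doubtful:

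- Five people give a very imprecise correlation, and the rule uses the point estimate alone.
- An ordinary correlation measures linear association, not agreement. It is blind to everyone moving by the same amount, which is the kind of drift that a before/after comparison needs to know about.
- Many items are yes/no, and with five respondents the coefficient is often undefined or takes only a few values.

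At stake is whether a report could properly say that the responses were shown to be consistent.

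**Working it through.** **Inputs from the documents (Section 3.2):** n of at most 5 per questionnaire; cut-off 0.70; 50-60 public and 30-40 provider items, yes/no or Likert. The documents derive neither the panel size nor the cut-off, so there is no figure of the plan's own to reproduce.

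**Assumptions:** true reliability (rho) is not given, so a range of 0 to 0.9 is used. Pass rates for rho above 0 come from simulated bivariate normal data (200,000 replicates). The coefficient is taken to be an ordinary correlation.

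**1. Precision, per-item reading.** Fisher interval: tanh(atanh(r) ± 1.96/√(n − 3)).

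- r = 0.70, n = 5: atanh(0.70) = 0.867; 1.96/√2 = 1.386; tanh(−0.519) to tanh(2.253) = **−0.48 to 0.98**.
- r = 0.90, n = 5: 0.09 to 0.99.
- r = 0.70, n = 4, since the provider panel is only capped at five: −0.80 to 0.99.

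The two-sided 5% critical value of r at n = 5 is 3.182/√(3.182² + 3) = 0.878. A coefficient just above 0.70 is therefore not distinguishable from zero correlation.

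**2. Chance of passing (r > 0.70), n = 5.** For rho = 0 it is exact: t = 0.70 × √3/√(1 − 0.49) = 1.70 on 3 df, upper tail 9.4%.

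| True rho | 0 | 0.3 | 0.5 | 0.7 | 0.8 | 0.9 |
|---|---|---|---|---|---|---|
| Chance of passing | 9% | 21% | 35% | 58% | 73% | 90% |

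If every public item had rho 0.5, about 50 × 0.354 = 18 to 60 × 0.354 = 21 items would be read as consistent. At rho 0.8, about 100 − 73 = 27% would not be. With 5-point Likert answers (assumed category shares) the pass rates are 33% at latent rho 0.5 and 82% at 0.9.

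**3. Pooled reading.** Suppose 55 items and 5 people enter one coefficient and within-item reliability is zero. The expected correlation is then roughly s²/(s² + 1), where s is the between-item SD divided by the within-item SD. For s = 1.5 this is 2.25/3.25 = 0.69; for s = 2 it is 4/5 = 0.80. Simulation gave means of 0.68 and 0.79, with 41% and 99% of runs above 0.70. At s = 1 the mean was 0.49 and no run passed. Differences in item means can thus produce a pass, and the single coefficient says nothing about any one item.

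**4. Association is not agreement.** Likert answers 1, 2, 2, 3, 4 followed by 2, 3, 3, 4, 5 give r = 1.0 with 0 of 5 exact agreements. The mean signed change is +1.

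**5. Yes/no items.** If all five people give the same answer on either occasion, the variance is zero and r is undefined, even when agreement is perfect. If one of five answers changes, r is 0.61 or 0.67 (both below the cut-off) or undefined. With 80% answering yes, 42-55% of items have no defined coefficient over latent rho from 0.9 down to 0.

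**The case against.** The strongest reply is that this is a small pretest that feeds no hypothesis test, sample size or coverage estimate, and that the per-item reading is an inference. The plan speaks of responses, not items. If r were computed for one respondent across about 55 items, treated as independent, the same formula gives tanh(0.867 ± 1.96/√52) = 0.53 to 0.81. That stands as to precision, so the per-item figures are conditional. It does not rescue the rule, because spread between items inflates such a coefficient too.

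A reader might infer more than the documents support:

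- **That the rule cannot tell reliable from unreliable items.** It passes 9% at rho 0 and 90% at 0.9. It fails near 0.70, not everywhere.
- **That good items will be thrown out.** Elimination or revision in Section 3.2 belongs to the expert content-validity panel. Nothing is dropped because of the retest.
- **That the description of the instruments as validated has no support.** Reuse of validated questions, an earlier survey design and the expert panel all bear on validity. They do not measure repeatability, and that is the only gap here.
- **That KABB results will be biased.** No effect on any estimate is shown. Zero-mean error in a Likert item widens a group mean without shifting it, and the control communities are surveyed too.
- **That kappa or an intraclass correlation would cure the problem at n = 5.** Kappa is also undefined when all answers are identical, and both are imprecise. In the shift example above, the absolute-agreement intraclass correlation is still 0.72.

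A retest of about 30 people per questionnaire is also not demanded. The documents give no precision target from which to derive that number, and the retested people would have to be recruited identifiably, apart from the anonymous survey.

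**Conclusion.** The point holds in a limited form. As written, a verdict of consistent would be an unsupported statement about the questionnaires used for a primary objective. Under the per-item reading, the rule admits about one item in three at true reliability 0.5 and misses about one in four at 0.8. Under the pooled reading, it can be met with no within-item reliability at all when item means differ enough.

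These sizes rest on assumed true reliabilities, bivariate normality, an ordinary rather than an agreement-type coefficient, and assumed between-item spreads for the pooled case. The blindness to a uniform shift and the undefined yes/no values need only the ordinary-correlation assumption. The coverage estimates from pharmacy, physician and distribution data are untouched.

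**What to change.** In Section 3.2:

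- Delete the sentence part that reads a coefficient above 0.70 as consistent.
- State the unit of analysis.
- Report exact percent agreement per item with its exact binomial interval. Even 5 of 5 has a lower 95% limit of 0.025^(1/5) = 48%, which shows openly how little five people can establish.
- For Likert items, add the mean signed change, which shows a uniform shift.
- For the overall knowledge score, report an absolute-agreement intraclass correlation with its interval, accepting that the interval will be wide.
- Describe the five-person retest as a pilot check of wording and feasibility, not as evidence of test-retest reliability.

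The cost is a wording change and a different summary of data that the plan already collects. The downside is a weaker stated claim about the instrument.
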